This pilot study has 2 components: 1) a cross-sectional assessment designed to estimate the prevalence of anaemia leading to donor deferral, the prevalence of ID and the prevalence of IDA among first-time donors, and 2) a longitudinal 2-arm parallel groups trial among first-time voluntary donors that compares haemoglobin levels at 4 months among those with ID or IDA who receive iron supplementation to those without ID or IDA who do not receive iron supplementation. The primary outcome will be haemoglobin levels at 4 months. Participants will be followed for a total of 6 months with study visits at 2, 4 and 6 months after the baseline assessment. Blood draws for FBC, peripheral film comment, Malaria rapid test and ferritin assessment and the administration of a structured questionnaire will occur at all follow-up visits.

The parallel group's component is designed as a non-inferiority trial for haemoglobin levels at 4 months. At baseline, the 2 groups will be determined based on the need for iron supplementation: all individuals with ID or IDA, who satisfy our eligibility criteria regardless of deferral status, will receive iron supplements while all others will not. While a high prevalence of ID and IDA is expected, enrolment will be staggered so that an equal number of participants from each group are enrolled from each site with at least 1 participant who is found to be ID or have IDA. If there are more potential participants in one group at some site, randomization will be used to select the individuals to enroll in the trial to maintain balance over time. The extent of adherence is a central question for this study, and it is also unclear if the haemoglobin deficiency can be improved above what is seen in the control group, hence it is not hypothesized that those receiving

iron supplementation will have higher levels of haemoglobin at 4 months. The hypothesis about iron supplementation intervention is that it will improve haemoglobin levels to near that seen among those who were not deferred. If haemoglobin levels are higher in those receiving iron supplementation the intervention would also be deemed a success. Hence a non-inferiority trial is most appropriate for this hypothesis.

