Anaemia is a state in which the amount of red blood cells (RBCs) is insufficient to meet the body's physiologic needs ²⁴. Mild anaemia is defined as Hb ranging from 11-12.9 g/dL in adult males and 11-11.9 g/dL in adult females. Moderate anaemia is defined as Hb level of 8-10.9 g/dL and severe anaemia is defined as Hb level of less than 8 g/dL for all the age groups ^{25,26}.

Following FBC and plasma ferritin estimation, screened participants will be classified by the WHO criteria as shown in Table 4:

Table 4: Definition of Iron Status Criteria

| Haemoglobin concentration, g/dL | Plasma ferritin concentration µg/L | Interpretation |
|--|------------------------------------|---|
| [Male] >13.0 [Female] >11.5 | < 15 | Iron deficiency without anaemia |
| [Male] ≥8.0-13.0 [Female] ≥8.0-11.5 | < 15 | Iron deficiency with mild to moderate anaemia |

| | | | |
|-------|------|------|-------------------------------------|
| [All] | <8.0 | < 15 | Iron deficiency with severe anaemia |
|-------|------|------|-------------------------------------|

Schedule of Assessments (Table 5)

| Assessment | Screening (Day -14 to 0) | Enrolment (Day 0) | Biweekly (Throughout) | Interim Visit 1 | Interim Visit (Week 8-10) | Interim Visit 2 | Final Visit (Week 24) |
|--|-----------------------------|----------------------|--------------------------|--------------------|------------------------------|--------------------|--------------------------|
| NBSG Pre-Donation Assessment | X | | | | | | X |
| Informed Consent | X | | | | | | |
| Inclusion and Exclusion Criteria | X | | | | | | |
| Demographics | X | | | | | | |
| Full Blood Count and peripheral blood comment | X | | | X | X | X | |
| Plasma Ferritin | X | | | X | X | X | |
| Malaria Parasites Testing (RDT) | X | X | | X | X | X | |
| Nutritional Counselling | | X | | X | X | X | |
| Qualitative Assessment | | | | | | | X |
| Follow-Up Calls | | | X | | | | |
| Return Blood Donation Status | | | | X | X | X | X |
| Assessment for Adverse Events | | X | X | X | X | X | X |
| Adherence Assessment (for those receiving supplemental iron) | | | X | X | X | X | X |
| RDT – Rapid Diagnostic Test | | | | | | | |

Enrolment

Participants will be re-assessed with their laboratory results at the Day 0 visit.

- ***Eligibility Check***

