Participants will be followed up every 2 months and will be interviewed by members of the research team and appropriate CRFs completed by study staff. Adherence to iron supplementation and nutritional counseling will be assessed biweekly by phone and at each visit.

Participants with suspected adverse events of iron supplementation will be appropriately managed. Participants with suspected bacterial infections will be assessed with blood cultures (if indicated) and tested for malaria parasites during study visits. Malaria preventive measures will be discussed with all study participants on enrolment, and they will be encouraged to use these preventive measures throughout the study. A history of medical events and selected potential adverse events will be obtained at each scheduled visit and during biweekly follow up phone calls. Participants will also be given identification cards to carry with them at all times providing instructions directed to any health care provider who sees them for an unscheduled medical care visit.

- ***Treatment***

The planned duration of treatment is 4 months. Participants with a low plasma ferritin <15 μ g/L, with or without anaemia, will be given oral iron supplementation and nutritional counseling. Treatment will continue for 16 weeks or until the end of follow-up, during which participants will be followed up for adherence counseling at each visit. Clear written instructions for use 3 times a week will be discussed with them. Research staff will contact participants every 2 weeks by phone for adherence and feedback, and to remind participants to keep their scheduled study visits.

Testing of plasma ferritin and FBC after 4 months of supplementation will allow us to assess for response to study treatment with regards to iron stores. After correction of iron depletion or IDA, FBC and plasma ferritin will be monitored at 4 months from baseline. Participants after the end of the intervention phase still found to be iron deficient or anaemic will continue management and further evaluation at the haematology clinic.

- **Discontinuation**

If discontinuation of study treatment occurs, the investigator should make a reasonable effort to understand the primary reason for the participant's premature discontinuation of study treatment and record this information.

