The parallel group's component is designed as a non-inferiority trial for haemoglobin levels at 4 months. At baseline, the 2 groups will be determined based on the need for iron supplementation: all individuals with ID, IDA or low haemoglobin (gender specific values), who satisfy our eligibility criteria regardless of deferral status, will receive iron supplements while all others will not. While a high prevalence of ID and IDA is expected, enrolment will be staggered so that an equal number of participants from each group are enrolled from each site with at least 1 participant who is assigned to iron supplementation. If there are more potential participants in one group at some site, randomization will be used to select the individuals to enroll in the trial to maintain balance over time. The extent of adherence is a central question for this study, and it is also unclear if the haemoglobin deficiency can be improved above what is seen in the control group, hence it is not hypothesized that those receiving iron supplementation will have higher levels of haemoglobin at 4 months. The hypothesis about the iron supplementation intervention is that it will improve haemoglobin levels to near that seen among those who did not receive iron supplementation. If haemoglobin levels are higher in those receiving iron supplementation the intervention would also be deemed a success. Hence a non-inferiority trial is most appropriate for this hypothesis.

Selection of the margin is a critical component of a non-inferiority trial. Here, we specify a margin of 1 g/dL for haemoglobin levels at 4 months. Under a collection of reasonable assumptions, this margin will ensure that the majority of those with low haemoglobin at screening will have haemoglobin levels at 4 months above the threshold for anaemia and should therefore qualify as donors. To see this, assume that half of donors are anaemic at screening (using the thresholds for anaemia of 13 g/dL for men and 11.5 g/dL for women). A simple calculation finds that if we assume haemoglobin levels are normally distributed (which is a reasonable assumption based on observed distributions for haemoglobin in unselected individuals in West Africa) and the standard deviation of screening haemoglobin levels is 1.89 g/dL (this estimate will be described below) then the mean haemoglobin level among men who are deferred is 11.5 g/dL and the mean haemoglobin level among men who are not deferred is 14.5 g/dL (these values for

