women are 10.0 g/dL and 13.0 g/dL). If we assume that the haemoglobin level among those who are not deferred is the same 4 months later then a margin of 1 g/dL implies a mean haemoglobin level among those with anaemia at screening of at least 13.5 g/dL for men and 12.0 g/dL for women. Thus, the mean haemoglobin level after 4 months of iron supplementation among those who should have been deferred will exceed the threshold for anaemia and consequently, if the distribution of haemoglobin levels is symmetric, the majority of those who were anaemic at screening would qualify as donors (in fact at least 60.4% would pass the threshold for both sexes if this distribution is normal). Note that the threshold for the copper sulphate test used for women is 12 g/dL, not 11.5 g/dL, so under these assumptions 50% of women would pass the copper sulphate test. Nonetheless, since well over 50% of donors are men the majority of deferred donors would pass the copper sulphate test. It is likely that fewer than half of all donors will be anaemic at screening. In this case the difference in the means between those with anaemia and those without anaemia will be larger, the gain in haemoglobin levels in the anaemic group will be larger and the proportion of donors who would be deferred at screening but would not be deferred after 4 months of iron supplementation will be even larger. It is possible that the difference between the 2 groups is smaller than the margin at screening. This seems unlikely since the 2 groups are defined by a threshold for haemoglobin levels, but if the standard deviation of haemoglobin levels is 0.62 then the difference between the groups among men would be less than the margin under the assumptions of the previous paragraph (this standard deviation is less than one third of the standard deviation used for design). To address this, when enrolment reaches 50% of the total planned sample size, the statisticians supporting the trial at the data coordinating centre (DCC) will compute the standard deviation of haemoglobin levels at screening and revisit the margin calculation and the sample size. If the standard deviation is low enough so that the difference between the groups is less than the margin, then the study will be overpowered for the current margin and a smaller margin will be selected so that the trial is still testing for differences at 4 months that exceed the screening difference. Any changes to the study design based on these analyses will be discussed with the DSMB.

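### The margin rationale and the 50%-enrolment check assume arms split at a haemoglobin threshold, but the arms are formed partly or wholly on iron status

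*SAP*

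**What the plan says.** **How the arms are formed.** Protocol, Design: "all individuals with ID or IDA, who satisfy our eligibility criteria regardless of deferral status, will receive iron supplements while all others will not". Protocol, Treatment (under Follow Up Assessments): donors with low ferritin, "with or without anaemia, will be given oral iron supplementation and nutritional counseling". Protocol Table 4 has a class "Iron deficiency without anaemia". The SAP is wider: "all individuals with ID, IDA or low haemoglobin (gender specific values), who satisfy our eligibility criteria regardless of deferral status, will receive iron supplements" (1.2, Design), and SAP section 4 agrees.

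**How the margin is justified.** The SAP says, under assumptions it calls reasonable, that "this margin will ensure that the majority of those with low haemoglobin at screening will have haemoglobin levels at 4 months above the threshold"; the cut-off meant is the one that defines anaemia. The calculation splits donors at 13 g/dL (men) or 11.5 g/dL (women), with half below and SD 1.89. It arrives at a pass rate of at least 60.4%. The protocol's Design section has the same argument.

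**The check.** Both documents ask whether the screening gap could be smaller than the margin and answer "This seems unlikely since the 2 groups are defined by a threshold for haemoglobin levels". At 50% enrolment the coordinating centre will "compute the standard deviation of haemoglobin levels at screening and revisit the margin calculation and the sample size". The written trigger is "If the standard deviation is low enough so that the difference between the groups is less than the margin", with 0.62 as the reference SD. The action is a smaller margin, discussed with the DSMB.

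**The null hypothesis.** Protocol (Sample size justification) and SAP 2.4 state it as treated donors with low haemoglobin against untreated donors without it.

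**The concern.** There are three descriptions of who is compared: the protocol's assignment rule, the SAP's assignment rule, and the pure haemoglobin split used for the margin and the null. Under either assignment rule a donor with low ferritin and normal haemoglobin goes to the iron arm. Under the protocol rule an anaemic donor who is not iron deficient goes to control.

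Two things depend on this. First, the reason given for 1 g/dL is that an iron-arm mean within 1 g/dL of control implies that most anaemic donors would qualify. If the iron arm also holds non-anaemic donors, the margin applies to a mixed mean, and the anaemic members can sit more than 1 g/dL below control while the arm as a whole meets the margin. Second, the sponsors saw that a margin wider than the screening gap would be a problem and planned a safeguard. That safeguard infers the gap from the SD, and the SD determines the gap only under a pure split.

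**Working it through.** **Inputs from the documents.** SD 1.89, thresholds 13 and 11.5, half below threshold, margin 1 g/dL (Design, both documents); 1:1 arms (Design); Hb <10 g/dL excluded (Exclusion Criteria); 48% anaemic, of whom 86.1% ID, and 68.8% ID overall in a second unpublished study (Protocol, Problem Statement).

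**Assumptions not in the documents.** Non-anaemic ID donors have the same haemoglobin as other non-anaemic donors; among anaemic donors, haemoglobin does not depend on ID; the two studies can be combined; the pooled prevalences apply to each sex.

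**Step 1: reproduce the plan.** The half-normal shift is 1.89 × √(2/π) = 1.508. Means are 11.49 and 14.51 (men), 9.99 and 13.01 (women), so the gap is 3.02. With the anaemic mean 0.5 above threshold, Φ(0.5/1.89) = 60.4%. Under a pure split, gap = 2 × SD × √(2/π): 0.99 at SD 0.62, and exactly 1 at SD 0.627. The plan's arithmetic is right on its own premise.

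**Step 2: pass rate at the margin, SAP rule.** Let f be the non-anaemic share of the iron arm. If the arm mean is control minus 1, the anaemic members' mean is control − 1/(1−f). With control 1.5 above threshold, as in the plan's rounded means, pass rate = Φ((1.5 − 1/(1−f))/1.89), the same for both sexes.

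| f | Pass rate |
|---|---|
| 0 | 60.4% |
| 0.2 | 55.3% |
| 0.3 | 51.5% |
| 1/3 | 50.0% |
| 0.5 | 39.6% |

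*Where f might lie.* Anaemic and ID: 0.48 × 0.861 = 0.413. This is also the 41.3% overall ID used in the sample-size section, which leaves no non-anaemic ID donors, so f = 0. With 68.8% ID, non-anaemic ID = 0.688 − 0.413 = 0.275, f = 0.275/(0.275 + 0.48) = 0.36, and about 49% pass.

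*Sensitivity.* At f = 0.36, a mean only 0.11 g/dL lower in non-anaemic ID donors, or enrolling anaemic donors 1.13 times as often, brings the rate back to 50%.

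**Step 3: screening gap and SD, Hb <10 removed.** With Hb <10 removed, the anaemic mean L is 11.78 (men) or 10.79 (women), and 88.8% or 57.3% of anaemic donors remain. The non-anaemic mean U is 14.51 or 13.01, so U − L = 2.725 or 2.22. Let g be the anaemic share of controls. Then gap = (1 − f − g)(U − L), and SD of the 1:1 sample = √(mean within-arm variance + gap²/4).

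| Rule | Sex | f | g | Gap (g/dL) | SD |
|---|---|---|---|---|---|
| SAP | Men | 0.392 | 0 | 1.66 | 1.63 |
| SAP | Women | 0.500 | 0 | 1.11 | 1.39 |
| Protocol | Men | 0.428 | 0.194 | 1.03 | 1.67 |
| Protocol | Women | 0.537 | 0.135 | 0.73 | 1.41 |

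Example, men, protocol rule: f = 0.275/(0.275 + 0.413 × 0.888) = 0.428. Anaemic controls are 0.48 × 0.139 × 0.888 = 0.059 and non-anaemic controls 0.52 − 0.275 = 0.245, so g = 0.194. The gap is 0.378 × 2.725 = 1.03.

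The protocol rows are before any control who later starts iron is excluded. If every anaemic control were excluded (g = 0), the gaps would be 0.572 × 2.725 = 1.56 and 0.463 × 2.22 = 1.03. Under the SAP rule the gap drops below 1 only if f exceeds 1 − 1/(U − L) = 0.63 (men) or 0.55 (women).

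In all four rows the SD is more than twice 0.62, so the trigger stays silent even where the gap is 0.73.

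**The case against.** The best case for the plan has several parts.

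- The margin claim is introduced as holding under a collection of assumptions, so it is an illustration and not a guarantee. This stands, but the listed assumptions do not include an all-anaemic iron arm, and the SAP's own assignment rule contradicts one.
- A majority does not need a pure split; only the figure 60.4% does. This stands. A reader might infer from the mismatch that the majority statement is false, but the documents do not support that. The 41.3% figure gives f = 0, and losing the majority needs a second study's prevalence plus control-like haemoglobin in non-anaemic ID donors. The protocol's Introduction describes ID as progressing towards anaemia, which points to somewhat lower values. The SAP also plans to over-approach donors who fail the copper sulphate test (Stratification and Sampling), which would raise the anaemic share.
- A sub-margin gap appears only for women, under the protocol rule, before exclusions, and with pooled prevalences applied by sex. This stands. The documents do not show such a gap to be likely under the SAP rule.
- The coordinating centre will revisit the margin calculation, and baseline characteristics by group go into the closed DSMB report (SAP 3.4). This leaves room to look at the observed gap, but no written rule uses it.
- The primary model adjusts for screening haemoglobin (SAP 7.2.1). A reader might infer that the primary test is biased or its error rate wrong. Nothing here shows that: the margin argument is written on unadjusted means, and so is this check of it.

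**Conclusion.** The premise is wrong as written in both documents, and this needs no numerical assumption. The 60.4% applies only if every iron-arm participant is anaemic and no control is. Under the SAP rule, with control-like haemoglobin in non-anaemic ID donors, the majority holds until about one third of the iron arm is non-anaemic, so it depends on a mix the plan does not state.

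The safeguard uses a statistic that does not determine the gap for the arms as formed. In the illustration the gap is about 1.0 (men) and 0.7 g/dL (women) under the protocol rule, and 1.7 and 1.1 under the SAP rule, with SD 1.4 to 1.7 throughout. These sizes rest on two unpublished prevalence studies and on the assumptions listed above. The planned sample size of 292 is not in question. The point should be corrected, with medium confidence in its practical size.

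**What to change.** 1. **Check at 50% enrolment.** Replace the SD-inferred gap with the observed between-group difference in mean screening haemoglobin: sex-adjusted as the main figure, by sex as description, each with a 95% CI. Report the anaemic share of each arm. Apply the plan's existing action (smaller margin, discussion with the DSMB) when the sex-adjusted difference is below the margin.
2. **Margin text.** Correct the threshold premise in both documents and state that 60.4% applies only to a pure split. Support the majority statement with an estimate and 95% CI of the proportion of iron-arm participants with low screening haemoglobin who are at or above the sex-specific threshold at 4 months.
3. **Arm definition.** Reconcile it across the protocol, the SAP and the null hypothesis. This review does not say which rule is right.

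**Cost.** Wording only; the data are already collected.

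- *Precision of the gap.* With 292/4 = 73 per arm and within-arm SDs of 1.14 (control) and 1.63 or 1.40 (iron), the half-width is 1.96 × √((1.14² + 1.63²)/73) = 0.46, or 0.41. If 70% are men (an assumption), it is about 0.55 for men (51 per arm) and 0.76 for women (22 per arm).
- *Precision of the proportion.* It uses only part of the iron arm: of 131, about 83 at f = 0.36 (half-width 11 points) against 131 at f = 0 (9 points).
- *Sample size.* The plan says a study that triggers the check will be overpowered. That follows from a low SD, not from mixed arms. By the plan's formula, n scales with 1/(margin − 0.3)². With SD 1.89 and a true difference of −0.3 unchanged, a margin of 0.7 would need 131 × (0.7/0.4)² = 401 per arm, so the DSMB discussion should cover sample size too.

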## **Objectives**

### **Primary Objectives**

The primary objective of the Iron Supplementation Trial is to determine the potential for an iron supplementation strategy to increase blood donations in Ghana. To determine this potential, the study will investigate the feasibility and acceptability of this intervention along with key return blood donation measures among first-time blood donors found to have low haemoglobin or found to have IDA or be ID within the catchment areas of the SZBC. These aspects of the potential for this intervention will be

operationalized as follows:

- **Feasibility** of recruitment, enrolment, retention, and adherence will be evaluated with a target retention rate > 90% of all participants recruited completing the trial. If we are unable to achieve this target, alternative strategies will be considered for the UH3 phase.
- **Acceptability** will involve establishing the safety profile of 3 times weekly low dose ferrous sulphate (65mg elemental iron) supplements among those assigned to iron supplementation at enrolment. This safety profile will be established by comparison to a similar group of participants who do not receive iron supplementation. Participant and key informant views and perspectives of barriers and recommendations for using iron supplementation and nutritional counselling to increase the blood donor pool will also be investigated with participant questionnaires. In addition, FGDs and key informant interviews will provide critical insights into the acceptability of this intervention.
- **Key blood donation measures** include haemoglobin levels at 4 months, the change in haemoglobin concentration, ferritin levels at 4 months, the proportion of participants with corrected ID, the proportion of participants who return to the blood centre to donate blood and the proportion of returners who are able to successfully donate (not deferred). In addition, the incidence of ID and IDA among blood donors will be determined among those who consent to the Iron Supplementation Trial at screening.

To achieve this objective, a pilot parallel groups trial will be conducted for one year. This allows for enrolment over a maximum of 6 months and 6 months of follow-up for the last individual enrolled. The follow-up period incorporates 4 months of the iron supplementation intervention.

The **primary endpoint for the parallel groups trial** will be haemoglobin levels at 4 months, and this will be compared between those assigned iron supplementation at enrolment and those not assigned iron supplementation at enrolment.

